#### 5.4 Duration of Follow Up

Each subject should be followed for at least 30 ( $\pm 7$ ) days after his or her last dose of lenalidomide (i.e. the “safety follow-up period”) to monitor for resolution or progression of AEs and to document the occurrence of new events unless the subject receives a new CLL therapy within this time frame.

Subjects who withdraw consent should still be encouraged to complete the safety follow-up assessments, but these assessments cannot be mandated once consent is withdrawn. Patients removed from study for unacceptable adverse events will be followed until resolution or stabilization of the adverse event.

Beyond the safety follow-up period, patients no longer receiving protocol therapy will continue to be evaluated at 3 month intervals for the first year and every 6 months thereafter until they receive a new CLL therapy, withdraw consent, or expire. Patients may remain in follow-up if disease progression occurs. Required historical, laboratory, and physical examination procedures at each follow-up visit are detailed in the **Study Table** ([Section 10](#)).

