- i. Risk stratification studies will include serum  $\beta$ 2-microglobulin in addition to tests performed on the screening bone marrow biopsy specimen: IgVH mutational analysis (unless already known), interphase cytogenetics, stimulated karyotype and standard CLL FISH panel.
- j. Allopurinol should be administered beginning 3 days before first lenalidomide administration and continued through the first cycle of lenalidomide treatment in its entirety. Allopurinol can be continued during subsequent cycles at the treating physician's discretion.
- k. Thromboprophylaxis should begin with lenalidomide in patients at high-risk for venous or arterial thromboembolism (see [5.2.3](#)).
- l. Only enough lenalidomide for 28 days or one cycle of study treatment (whichever is shorter) may be provided to the patient each cycle.
- m. CBC is checked on D1 and D8 during the first cycle of lenalidomide exposure and during the second cycle and/or any subsequent cycle in which the dose of lenalidomide has been escalated. CBC should be checked weekly during any subsequent cycle in which the dose of lenalidomide has been reduced for hematologic toxicity.
- n. Response is assessed clinically (CBC, physical examination) after every 2 cycles of lenalidomide treatment beginning with Cycle 3 (Arm A) or Cycle 5 (Arm B), respectively. For patients meeting clinical criteria for CR for  $\geq$  2 months, bone marrow biopsy and CT scans should be performed to confirm response.
- o. The End of Therapy visit is defined as that occurring after 24 cycles. Patients discontinuing treatment at other times secondary to toxicity, progression, or preference only need the clinical assessment (except informed consent and education and counseling) and a complete blood count. Patients discontinuing for any reason are followed for at least 30 days to ensure resolution of any adverse events; however, these patients will still be followed for outcome until meeting criteria outlined in footnote "p" below.
- p. Patients no longer receiving active treatment are followed every 3 months during the first year and every 6 months thereafter until the patient receives a new CLL therapy, withdrawal of consent, or death.
- q. Unless completed within the last month.
- r. CT scans of the chest, abdomen, and pelvis.

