#### **13.5 Analysis of Secondary Endpoints**

In addition to evaluating the proportion of patients who have a vaccine-related antibody response to PCV13, we will also evaluate the seroconversion rates and antibody titre levels for each of the serotypes of the 13-valent pneumococcal vaccine. These markers will be summarized using descriptive statistics by treatment arm. We will graphically evaluate changes in these serotype-specific markers between the two arms, and we will also use the nonparametric Mann-Whitney rank sum test to compare the geometric mean concentrations.

Secondary endpoints will also include the CR rate following 2 years of lenalidomide treatment. Assuming that the number of CRs is binomially distributed, then we will also generate corresponding 95% confidence intervals for the CR rate estimate. If there is also a significant difference between the arms in terms of the vaccine response to PCV13, then we will also compare the CR rates between the two arms in an exploratory manner, although we will only be able to detect a large differential in CR rates (10% vs. 40%) with at least 80% power and a Type I error rate of 10%. In addition, we will evaluate time to event outcomes such as time to first treatment (TFT) and overall survival (OS). TFT will be defined as the time from study entry to first therapy for progressive CLL as defined by IWCLL 2008 criteria. To evaluate this endpoint, patients will be followed even after discontinuing therapy, where we will document date of subsequent treatment and/or progressive disease. Survival will also be evaluated, although we do not expect

many events in this early stage, asymptomatic group of patients. Time to event outcomes will be summarized and explored between treatment arms using Kaplan-Meier methods. Formal comparison of these endpoints between the two arms will not be done due to lack of statistical power to do so. In a very exploratory manner, we will also assess time to treatment in relation to the results reported by Shanafelt et al (2009); in an exploratory manner, we will utilize their prognostic scoring to identify an expected versus observed time to treatment.[64-65]

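### Overall survival is planned, but outcome follow-up stops at the next CLL therapy, and time to first treatment has two different starting points

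*Combined protocol and SAP*

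**What the plan says.** **Overall survival.** Section 13.5 states "we will evaluate time to event outcomes such as time to first treatment (TFT) and overall survival (OS"), to be summarised by Kaplan-Meier methods. It expects few deaths and plans no formal comparison between arms. It gives no censoring rule for OS.

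After protocol therapy, section 5.4 continues visits every 3 months for a year and then "every 6 months thereafter until they receive a new CLL therapy, withdraw consent, or expire". Footnote p of the study calendar repeats this: "every 6 months thereafter until the patient receives a new CLL therapy, withdrawal of consent, or death". Footnote o says of patients who stop early that "these patients will still be followed for outcome until meeting criteria outlined in footnote" p. Progression is not a stopping event: "Patients may remain in follow-up if disease progression occurs".

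The only follow-up commitment in 13.5 is attached to TFT: "patients will be followed even after discontinuing therapy, where we will document date of subsequent treatment and/or progressive disease".

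**Time to first treatment.** Section 13.5 says "TFT will be defined as the time from study entry to first therapy for progressive CLL". Objective 1.2.2 starts the clock at diagnosis instead, and counts only non-lenalidomide therapy as the event. That qualifier is absent from 13.5. Criterion 3.1.4 excludes anyone with prior CLL therapy.

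**The concern.** OS needs each patient's vital status up to a cut-off, whatever treatment follows. Here observation ends at a clinical event, the start of a new CLL therapy, that usually marks worsening disease. Deaths after it are mostly not collected. If patients who move to a new therapy then die at a different rate, censoring them there is informative and the curve does not estimate overall survival.

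TFT is a named secondary objective with two origins. Time between diagnosis and entry is free of treatment by eligibility, so starting at diagnosis gives every patient a stretch in which the event could not have been observed. The two definitions give different results, and the plan does not say which will be reported.

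**Working it through.** **1. Can deaths after a new CLL therapy reach the database?** The remaining routes are all safety reporting:
- The expedited-reporting table in 7.3.1 covers Grade 5 events of any attribution within 30 days of the last dose. Visits need not support this, because 5.4 has sites "document the occurrence of new events unless the subject receives a new CLL therapy within this time frame".
- Its footnote 1 covers later Grade 5 events, but only if at least possibly related to treatment.
- A note in 7.3.1 requires reporting of all deaths on study, without defining on study.
- Section 7.5.2.3 requires prompt IRB reporting of serious, unexpected, related events, even after study completion or withdrawal.

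None of these is survival follow-up.

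**2. Size of the OS effect.** The plan has no OS figure to reproduce and no hazards, so the rates below are assumptions: constant death hazard h0 before next therapy (0.01-0.02 per year), h1 after it (0.04-0.12), and median time to next therapy m of 2-5 years. The number of patients is 48 (maximum in 13.4).

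With g = ln2/m:
- True OS(t) = exp(-(h0+g)t) + g[exp(-h1·t) - exp(-(h0+g)t)]/(h0+g-h1)
- Kaplan-Meier limit when follow-up stops at next therapy: K(t) = exp(-h0·t)
- Greenwood variance (large sample): K² · h0 · [exp((h0+g)t) - 1]/[48(h0+g)]

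Low corner at 2 years (h0 = 0.02, h1 = 0.04, m = 5, g = 0.1386):
- True OS = 0.7281 + 0.1386 × (0.9231 - 0.7281)/0.1186 = 0.9560.
- K = 0.9608, an overstatement of 0.48 points.
- The Greenwood 95% half-width is 5.9 points.

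High corner at 2 years (h0 = 0.01, h1 = 0.12, m = 2, g = 0.3466):
- True OS = 0.4901 + 0.3466 × (0.7866 - 0.4901)/0.2366 = 0.9245 (unrounded inputs).
- K = 0.9802, an overstatement of 5.57 points.
- The half-width is 1.96 × sqrt(0.9802² × 0.01 × 1.0403/(48 × 0.3566)) = 4.7 points, so bias/half-width is 1.18.

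Over a grid of 315 combinations in these ranges, the bias exceeds the half-width at 4, all near the high corner.

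| Case | Bias in OS |
|---|---|
| h1 = h0, 2 years | 0 |
| h1 = 2-3 × h0, 2 years | +0.2 to +2.1 points |
| h1 = 0.04-0.12, 2 years | +0.5 to +5.6 points |
| h0 = 0.02, h1 = 0.01, m = 2, 2 years | -0.5 points |
| Low corner, 6 years | +3.3 points (85.4% true, 88.7% shown) |
| High corner, 6 years | +28.3 points (65.8% true, 94.2% shown) |

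**3. Deaths not collected by 2 years.** Total deaths are 48(1 - OS); collected deaths are 48·h0/(h0+g)·[1 - exp(-(h0+g)t)].
- Low corner: 2.11 - 1.65 = 0.47 lost (22% of deaths).
- High corner: 3.62 - 0.69 = 2.94 lost (81%).
- Equal hazards: 0.1-0.5 lost (13-28%).

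Even if new therapy began the day after the last lenalidomide dose, the 30-day rule would recover 48 × P(next therapy by 2 years) × [1 - exp(-h1 × 30/365.25)]. That is 0.04 deaths at the low corner and 0.23 at the high corner, about 8% of those lost.

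**4. TFT.** For each patient, TFT under 1.2.2 = TFT under 13.5 + (entry date - diagnosis date). The documents do not give that interval. As an illustration, a patient diagnosed 1 year before entry and treated 2 years after entry has a TFT of 3 years under 1.2.2 and 2 years under 13.5.

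**The case against.** OS is peripheral. It is not among objectives 1.2.1-1.2.6 or in the 13.1 overview, and 13.5 already warns of few deaths and declines a formal comparison. Nothing says in words that OS will be censored at next therapy. Section 9 says the study endpoints have been met and few patients remain on treatment, so new data collection could look like a preference. All of this limits the severity. It does not remove the conflict: footnote o applies the stop to outcome follow-up, not only to clinic visits, and no other section supplies later vital status.

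A reader might infer more than the documents support:
- *The OS curve will be too high.* This is plausible: section 2.4 describes a subgroup at high risk of progressing early and then dying of the disease. But it does not compare hazards before and after next therapy. Section 7.1 also notes higher mortality on single-agent lenalidomide than on chlorambucil in a first-line CLL trial. That is a different setting, but it leaves the direction open.
- *Deaths after progression are lost.* They are not, as long as no new CLL therapy has started.
- *No death after new therapy is ever reported.* Some would be, through safety reporting.
- *Any bias is within sampling error.* This usually holds at 2 years under the assumed rates, but not at the extreme corner.
- *The TFT analysis in 13.5 is inflated.* It is not; the problem arises only under the 1.2.2 definition.

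On TFT, 13.5 also plans an exploratory comparison of observed with expected time to treatment using a published prognostic score. That score's origin cannot be seen here, so diagnosis may be needed for that one comparison.

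**Conclusion.** Both conflicts stand, as a minor point. As written, the plan yields a curve labelled overall survival that does not follow patients past their next CLL therapy, and a secondary objective with two origins.

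The sign and size of the OS error rest on hazards that the documents do not give. It grows with time when the later hazard is higher. No data cut-off is stated; with a projected start of 01/01/2011 and a version dated March 15, 2024, follow-up well beyond 2 years is possible, although actual accrual dates are not given.

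The TFT discrepancy equals each patient's diagnosis-to-entry interval and is otherwise unquantified; the difference in event wording matters little in practice. The primary endpoint, sample size and CR decision rule are untouched.

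**What to change.** **OS.** Either of two changes is sufficient:
- In 5.4 and footnote p, add that after a new CLL therapy vital status and date of death are still collected, by record review or brief contact and subject to consent, until death, withdrawal of consent or a stated cut-off. In 13.5, define OS from study entry to death from any cause, censored at the last date known alive.
- With no new data, replace OS in 13.5 with time from study entry to next CLL therapy or death, whichever comes first.

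The first option costs a short amendment and a vital-status check for at most 48 patients, much of it retrospective. Those already out of follow-up may need a consent check or re-contact, and some may remain unknown. The second costs only wording.

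**TFT.** Use one definition in 1.2.2 and 13.5: study entry as origin, and the non-lenalidomide qualifier on the event in both. If the prognostic-score comparison needs diagnosis as origin, keep it there only and handle delayed entry by left truncation. This needs no new data for the main definition; a diagnosis-based comparison needs diagnosis dates.

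Both changes should be made before any OS or TFT result is reported.

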#### 5.5 Criteria for Removal from Study

Patients will be removed from treatment when any of the criteria listed in [Section 5.3](#) applies. Irreversible or unacceptable treatment-related toxicities that are Grade  $\geq 3$  as listed in [Section 5.3](#) necessitate discontinuation from study treatment. A patient with a treatment-related Grade  $\geq 3$  adverse event that resolves to Grade  $\leq 1$  within 14 days may continue treatment with appropriate dose reductions as outlined in [Section 6](#). Any Grade 4 toxicity attributable to lenalidomide will require discontinuation from study treatment. The reason for study removal and the date the patient was removed must be documented in the Case Report Form.

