### 5.3 Duration of Therapy

Patients demonstrating clinical benefit, defined as achievement of an objective response (CR, CRi, or PR) or stable disease (SD), may continue therapy for up to 24 cycles (approximately 2 years) of treatment with lenalidomide. Therapy beyond 24 cycles may be considered after discussion with the principal investigator and consultation with the study sponsor.

Investigators are encouraged to keep patients experiencing clinical benefit on study unless significant toxicity puts the subject at risk or routine noncompliance puts the study outcomes at risk. If the subject meets any 1 of the following criteria, withdrawal from treatment is mandatory:

- Disease progression meeting 2008 IWCLL consensus criteria for treatment.
- Intercurrent illness that prevents further lenalidomide administration.
- Any treatment-related Grade 4 non-hematologic toxicity.
- Unacceptable and/or unmanageable Grade  $\geq 3$  toxicity attributable to lenalidomide.
- Any treatment-related hematologic or non-hematologic toxicity delaying treatment more than 14 days.

- Development of autoimmune hemolytic anemia (AIHA) or immune-mediated thrombocytopenia (ITP)
- Subject elects to withdraw from study or becomes pregnant.
- General or specific changes in the patient's condition rendering the patient unacceptable for further treatment in the judgment of the investigator.
- Subject is noncompliant with study procedures and/or scheduled evaluations.
- Investigator considers withdrawal to be in the best interest of the subject.
- Diagnosis of new or secondary malignancies after initiating treatment

Subjects with inadequate study drug compliance (i.e.  $\leq$  80% of planned doses administered) may be replaced.

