## 6. DOSING DELAYS/DOSE MODIFICATIONS

### 6.1 Dose Modifications due to Toxicity

Because this study assesses the benefits of treating early-stage, asymptomatic CLL/SLL patients who would not otherwise be receiving therapy, the definition of “unacceptable” toxicity will be defined as any treatment-related Grade 4 non-hematologic toxicity or any treatment-related Grade  $\geq 3$  toxicity deemed unmanageable or unacceptable by the patient, his or her treating physician, or the study chair. As described, in [Section 5.3](#) and [Section 5.5](#), unacceptable toxicity will require discontinuation of protocol therapy.

Subjects will be evaluated for adverse events at each visit with the NCI CTEP CTCAE version 5 used as a guide for grading of severity for both hematologic and non-hematologic toxicity.

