### 6.3.1 Hematologic Toxicity

- In the instance of Grade  $\geq 3$  lenalidomide-related hematologic toxicity on day 1 of a cycle, delay lenalidomide therapy and monitor CBC at least weekly. If toxicity resolves to Grade  $\leq 1$  within 2 weeks, then resume lenalidomide at the next lower dose level.
- If Grade  $\geq 3$  lenalidomide-related hematologic toxicity occurs during a cycle, delay lenalidomide therapy and monitor CBC at least weekly. If toxicity resolves to Grade  $\leq 1$  within 2 weeks, then resume lenalidomide at the next lower dose level.
- If treatment is delayed for more than 2 weeks, discontinue protocol therapy.
- WBC colony stimulating factors may not be used to avoid dose reductions but can be used in the treatment of febrile neutropenia as outlined in 6.3.2 below.
- Because of the potential to increase the risk for venous thromboembolic disease, the use of erythropoietic stimulating agents (ESAs) will not be permitted.
- Because a decrease in absolute lymphocyte count (and thus WBC count) is an expected therapeutic outcome of treatment with Lenalidomide, no dose modification is required for the AEs of White Blood Cell Decreased or Lymphocyte Count Decreased.

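### A Grade 4 hematologic toxicity attributed to lenalidomide that resolves within 14 days is a mandatory stop in Section 5.5 but not in Sections 5.3, 6.1, 6.3.1 or 6.3.2, and no section is said to govern

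*Combined protocol and SAP*

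**What the plan says.** All references are to the combined protocol and SAP.

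- **Section 5.5** ends its toxicity rules with "Any Grade 4 toxicity attributable to lenalidomide will require discontinuation from study treatment". It makes no exception for blood counts. The sentence before it says that a patient with a related Grade 3 or higher event that settles to Grade 1 or less within 14 days "may continue treatment with appropriate dose reductions as outlined in" Section 6.
- **Section 5.3**, the list of mandatory reasons for withdrawal, has a narrower Grade 4 entry: "Any treatment-related Grade 4 non-hematologic toxicity". Hematologic toxicity is named in a different entry, which depends on delay and not on grade: "Any treatment-related hematologic or non-hematologic toxicity delaying treatment more than 14 days". A further entry covers Grade 3 or higher toxicity judged unacceptable or unmanageable.
- **Section 6.1** says that unacceptable toxicity "will be defined as any treatment-related Grade 4 non-hematologic toxicity", or Grade 3 or higher toxicity that the patient, physician or study chair judges unacceptable or unmanageable. It cites both 5.3 and 5.5 for the consequence.
- **Section 6.3.1** covers Grade 3 or higher events, hence Grade 4. If "lenalidomide-related hematologic toxicity occurs during a cycle, delay lenalidomide therapy and monitor CBC at least weekly"; if it settles to Grade 1 or less "within 2 weeks, then resume lenalidomide at the next lower dose level". It adds that "no dose modification is required for the AEs of White Blood Cell Decreased or Lymphocyte Count Decreased", without a grade limit.
- **Section 6.3.2** gives the same hold-and-resume rule for febrile neutropenia.
- **The schema** has yet another formulation: treatment continues in the absence of irreversible Grade 3 or higher toxicity, hematologic or not.

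**The concern.** A physician faced with a Grade 4 neutropenia attributed to lenalidomide that recovers in ten days can cite one section for stopping the drug for good and another for restarting it one level lower. Either choice complies with part of the protocol and breaches another part. For a Grade 4 lymphocyte decrease the choice is between stopping and changing nothing.

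This is first a safety matter: the patients are asymptomatic and, as Section 6.1 says, would not otherwise be on therapy. It also bears on the data. Section 13.5 assesses time to treatment failure, which ends when treatment is discontinued, and summarizes the reasons for stopping. If the stopping rule depends on which section was read, both measures mix tolerability with the reader's choice. Time on lenalidomide also underlies the two-year CR rate in Section 13.3.

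**Working it through.** The point rests on a comparison of text. The plan gives no figure to reproduce.

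**Step 1. Action required for each event, if attributed to lenalidomide**

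| Grade 4 event | Section 5.5 | Sections 5.3 and 6.1 | Section 6.3 |
|---|---|---|---|
| Neutropenia or thrombocytopenia, Grade 1 or less within 14 days | Discontinue | No automatic stop | 6.3.1: hold, resume one level lower |
| Febrile neutropenia, recovered within 2 weeks | Discontinue | No automatic stop | 6.3.2: hold, resume one level lower |
| White cell or lymphocyte decrease | Discontinue | No automatic stop | 6.3.1: no dose modification |
| Hematologic toxicity delaying treatment more than 14 days | Discontinue | 5.3: withdraw | 6.3.1 and 6.3.2: discontinue |

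The first three rows conflict. In the fourth all sections agree. For white cell and lymphocyte decreases 6.3.1 itself calls for no hold, so the 14-day limit does not settle the matter by that route.

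**Step 2. Is there a rule of precedence?** None is stated. Section 6.1 cites 5.3 and 5.5 together although their scope differs. Sections 5.3, 5.6 and 6.1 all write non-hematologic where that limit is meant; the Grade 4 sentence in 5.5 does not.

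**Step 3. Is the conflict foreseeable?** Yes. The list of exceptions to expedited reporting in Section 7.1 names neutrophil, platelet, lymphocyte and white cell decreases at Grade 4. The March 2024 amendment added the white cell and lymphocyte exception to 6.3.1, while 5.5 still carries the unqualified Grade 4 stop.

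**Step 4. How many patients?** The documents give no Grade 4 hematologic rate at this dose. Assume 5-20% for all attributable Grade 4 hematologic events, and take the maximum accrual of 48 (Section 13.4):

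- 0.05 × 48 = 2.4
- 0.20 × 48 = 9.6

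That is about 2-10 patients. For a given rate it is an upper bound, because it includes patients whose events delay treatment beyond 14 days and who stop under every section.

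**Step 5. What could reach the CR analysis?** Suppose affected patients have the CR rates used in Section 13.3, 10% (null) to 25% (target):

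- 2.4 × 0.10 = 0.24 expected CRs
- 9.6 × 0.25 = 2.4 expected CRs

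Not all of these would be lost by stopping, so the effect on the CR count is smaller still.

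**The case against.** The strongest defense is that the sections can be read together. Section 6.3.1 is the specific rule for blood counts and might be taken to override a general sentence in 5.5. That is a reasonable guess at the intent, but the documents do not say so, and the unqualified wording of 5.5 points the other way. Sections 5.3 and 6.1 also leave room to stop for a Grade 4 cytopenia judged unacceptable, so they do not force continuation. That stands, but a stop by judgment is not the mandatory stop of 5.5.

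Several stronger readings are tempting, and the documents do not support them:

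- **Three rival actions for one event.** Each event has two. Holding and leaving the dose unchanged both come from 6.3.1 and apply to different events.
- **Section 5.5 contradicts itself.** Its last toxicity sentence can be read as a Grade 4 exception to the one before. The firm conflict is between sections.
- **Grade 4 events are common.** The risk list puts neutrophil and platelet decreases in its column for frequencies above 20%, but that column is not a Grade 4 rate, and the dose here is capped at 5 mg/day. Section 5.2.3 calls platelets below 50K unexpected.
- **The CR decision is at risk.** The threshold of 8 counts CRs among 44 patients. Setting 2-10 affected patients against it does not compare like with like, as Step 5 shows. Section 13.6.2 also keeps patients with treatment deviations in the response analysis.
- **Sites will differ.** The CTEP multicenter section is marked not applicable, and several treating sites are not established. Differences between patients or physicians are as far as one can go.
- **The primary endpoint is biased.** In Arm A lenalidomide precedes both vaccinations, but the documents do not say that stopping lenalidomide means dropping out before the booster.

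It is also fair to say that the time for prevention has largely passed. Section 9 reports that endpoints have been met and that few patients remain on treatment. Time to treatment failure and reasons for stopping are only described, with no formal test specified.

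**Conclusion.** The contradiction is real, is in current text, and is wrong as written. It is confined to Grade 4 hematologic events attributed to lenalidomide: those that resolve within 14 days, where 5.5 opposes 5.3, 6.1, 6.3.1 and 6.3.2, and white cell or lymphocyte decreases, where 5.5 opposes the exception in 6.3.1. Patients with the same event can be managed differently; the documents do not show that they were.

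The size is at most about 2-10 of 48 patients, resting wholly on the assumed 5-20% rate. The direct consequences are for patient safety and for the meaning of time to treatment failure and the reasons for stopping. Any effect on the two-year CR rate is unknown and probably small.

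**What to change.** Reconcile the schema and Sections 5.3, 5.5, 6.1, 6.3.1 and 6.3.2 to one rule for Grade 4 hematologic toxicity attributed to lenalidomide. State whether the white cell and lymphocyte exception and febrile neutropenia fall under it. Put the rule in one place and refer to it from the others. The sponsor and the investigator decide which rule applies; this review takes no view.

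For events that have already occurred, record which rule was applied to each patient, so that time to treatment failure and the reasons for stopping can be interpreted.

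The cost is amendment wording and a look back through the records of patients with such events. Section 5.5 already requires the reason for and date of removal to be documented. No change to sample size or analysis is needed.
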